6. INTERIM ANALYSES

There is no planned interim analysis for this study.

7. DATA REVIEW

7.1. Data Handling and Transfer

Data are entered electronically into a clinical database built by Prometrica and exported as SAS[®] datasets. Data analyses including summary tables, figures, and data listings are produced using SAS[®].

Medical conditions and AEs are coded using the Medical Dictionary for Regulatory Activities (MedDRA) version 18.0 or higher, to assign a system organ class (SOC) and preferred term (PT) to each AE. Prior and concomitant medications are coded to preferred drug names using the World Health Organization Drug Dictionary (WHODRUG) version 2015:03 or higher.

Clinical laboratory results and normal ranges will be provided as SAS datasets from the central clinical laboratory vendor. Protocol deviations and violations (PDVs) will be identified by the Sponsor prior to database lock and will be presented as data listings.

8. UNBLINDING

Not applicable since this is an open-label study.

9. STATISTICAL METHODS

The software used for all summary statistics and statistical analyses will be SAS[®] (SAS Institute, Inc.)¹ Version 9.2 or later.

Most continuous data will be summarized with the following descriptive statistics: number of observations, mean, SD, median, minimum, and maximum; interquartile ranges will be provided as appropriate. Categorical data will be summarized with frequencies and percentages.

Missing data will not be imputed.

Formal statistical tests will be not be conducted and thus no p-values will be reported.

For presentation of data, the mean and median will be presented to 1 decimal place greater than the original data, SD will be to 2 decimal places greater than the original data, and the minimum and maximum will have the same number of decimal places as the original data. The format for range will be “Min, Max”. Standard deviation will be abbreviated as “SD”.

Data that is collected in an early termination visit may be included in the calculation of summary statistics for the week the early termination visit falls into, as long as the visit falls within the time-frame of a scheduled visit as displayed in [Table 1](#). For example, if a subject has early termination visit 3 days prior to a previously scheduled week 12 visit, the data collected will be included in the calculation of summary statistics for week 12. If the diary data is collected from the site at this visit, the diary data would also be included in the calculation of summary statistics for week 12. If data is included for a study week as in this example above, it would not be included as part of the ‘early termination column’s’ summary statistics, i.e., data would only be used and included once in a summary statistic calculation, i.e., used only in calculation of summary statistics for week 12 in this example.

For certain variables (i.e., ESS, UPDRS III), subjects should complete these at the site during an “ON” state, per the protocol. The site should have only collected this data if the subject was in fact in the “ON” state. However, in cases where the site collected the data anyway (i.e., in “OFF” or “fluctuating”), we will treat all data that shows up in the database as if they followed the protocol, i.e., we will not check for the subject being in the “ON” state before including in summary statistics.

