7.2 Unified Parkinson's Disease Rating Scale (UPDRS)

The UPDRS is a scale that was developed as an effort to incorporate elements from existing scales to provide a comprehensive but efficient and flexible means to monitor PD-related disability and impairment ([Fahn et al, 1987](#)).

The scale itself has four components, largely derived from preexisting scales that were reviewed and modified by a consortium of movement disorders specialists (Part I, Mentation, Behavior and Mood; Part II, Activities of Daily Living [ADL]; Part III, Motor Examination; Part IV, Complications of Therapy). One of the core advantages of the UPDRS is that it was developed as a compound scale to capture multiple aspects of PD. It assesses both motor disability (Part II: ADL) and motor impairment (Part III: Motor Examination). In addition, Part I addresses mental dysfunction and mood, and Part IV assesses treatment-related motor and non-motor complications. Of all available clinical scales for the assessment of Parkinsonian motor impairment and disability, the UPDRS is currently the most commonly used.

Only Sponsor/Sponsor's designee-accepted raters may administer the UPDRS subscales in accordance with the requirements for background, experience in a research setting and training as documented on the Certificate of Rater Approval.

Patients will be instructed to have already taken their normally scheduled dose of levodopa and their IMP prior to arriving at the study site in order to have their UPDRS Part III evaluated in the ON state (within approximately 1 to 3 hours after taking their levodopa dose). UPDRS in the ON state will be measured at a time representative of the ON state in that patient, not in “best” ON. UPDRS Part III in OFF will not be evaluated.

An example of the scale is provided in [Appendix 15.1](#).

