3 = Severe disturbance of gait, requiring assistance.

4 = Cannot walk at all, even with assistance.

30. Postural Stability (Response to sudden, strong posterior displacement produced by pull on shoulders while patient is erect, with eyes open and feet slightly apart. Patient is prepared.)

0 = Normal.

1 = Retropulsion, but recovers unaided.

2 = Absence of postural response; would fall if not caught by examiner.

3 = Very unstable, tends to lose balance spontaneously.

4 = Unable to stand without assistance.

31. Body Bradykinesia and Hypokinesia (Combining slowness, hesitancy, decreased armswing, small amplitude, and poverty of movement in general.)

0 = None.

1 = Minimal slowness, giving movement a deliberate character; could be normal for some persons. Possibly reduced amplitude.

2 = Mild degree of slowness and poverty of movement which is definitely abnormal. Alternatively, some reduced amplitude.

3 = Moderate slowness, poverty or small amplitude of movement.

4 = Marked slowness, poverty or small amplitude of movement.

Indicate the patient's PD state during the examination:

1. "On" during exam
2. Fluctuated during the exam
3. "Off" during exam

Part IV. COMPLICATIONS OF THERAPY (In the past week)

A. DYSKINESIAS

32. Duration: What proportion of the waking day are dyskinesias present? (Historical information.)

- 0 = None
- 1 = 1-25% of day.
- 2 = 26-50% of day.
- 3 = 51-75% of day.
- 4 = 76-100% of day.

33. Disability: How disabling are the dyskinesias? (Historical information; may be modified by office examination.)

- 0 = Not disabling.
- 1 = Mildly disabling.
- 2 = Moderately disabling.
- 3 = Severely disabling.
- 4 = Completely disabled.

34. Painful Dyskinesias: How painful are the dyskinesias?

- 0 = No painful dyskinesias.
- 1 = Slight.
- 2 = Moderate.
- 3 = Severe.
- 4 = Marked.

35. Presence of Early Morning Dystonia (Historical information.)

- 0 = No
- 1 = Yes

B. CLINICAL FLUCTUATIONS

36. Are any “off” periods predictable as to timing after a dose of medication?

- 0 = No
- 1 = Yes

37. Are any “off” periods unpredictable as to timing after a dose of medication?

- 0 = No
- 1 = Yes

38. Do any of the “off” periods come on suddenly, e.g., over a few seconds?

- 0 = No
- 1 = Yes

39. What proportion of the waking day is the patient “off” on average?

- 0 = None
- 1 = 1-25% of day.
- 2 = 26-50% of day.
- 3 = 51-75% of day.
- 4 = 76-100% of day.

C. OTHER COMPLICATIONS

40. Does the patient have anorexia, nausea, or vomiting?

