AE, adverse event; BP, blood pressure; CGI-C, Clinical Global Impression of Change; C-SSRS, Columbia-Suicide Severity Rating Scale; d, day; ECG, electrocardiogram; eCRF, electronic case report form; ESS, Epworth Sleepiness Scale; ET, Early Termination; FSH, follicle stimulating hormone; IMP, investigational medicinal product; mMIDI, Modified Minnesota Impulse Disorders Interview; MMSE-II, Mini-Mental State Exam – Second Edition (MMSE-II); PD, Parkinson’s disease; PDQ-39, Parkinson’s Disease Quality of Life Questionnaire; PGI-C, Patient’s Global Impression of Change; UPDRS, Unified Parkinson’s Disease Rating Scale; V, Visit.

Footnotes

^a Screening period may not exceed 6 weeks.

^b Visit windows for scheduled visits after Baseline (V2) are in relation to the date of the Baseline Visit (V2).

^c Obtain and record BP and pulse measurements after at least 5 minutes supine rest and again after standing for approximately 1 minute and 3 minutes.

^d At Screening and Baseline (before dosing), obtain and record serial BP and pulse measurements after at least 5 minutes supine rest and again after standing for approximately 1 and 3 minutes, on 3 occasions approximately 10 minutes apart.

^e Optional activities (e.g., additional assessments for evaluation of AEs) that may be performed at the investigator’s discretion.

^f A resting supine 12-lead ECG will be collected after the patient has been in a supine position for a minimum of 5 minutes. Ensure the ECG is collected when the patient is not experiencing dyskinesia that would interfere with an adequate recording.

^g At Baseline, obtain three 12-lead ECGs (i.e., 3 serial readings, performed several minutes apart). Ensure the ECGs are collected when the patient is not experiencing dyskinesia that would interfere with an adequate recording.

^h To be collected during patient’s ON state.

ⁱ UPDRS to be measured in ON state. UPDRS Part III should be measured approximately 1 to 3 hours after patients have taken a scheduled dose of levodopa (preferably their morning dose of levodopa). Patients will be instructed to have already taken their normally scheduled dose of levodopa and their IMP before arriving at the study site in order to have their UPDRS Part III evaluated in the ON state. UPDRS in the ON state will be measured at a time representative of the ON state in that patient, not in the patient’s “best” ON.

Table 1: Schedule of Events/Evaluations (continued)

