5.5. Baseline Complete UPDRS Assessment

A valid UPDRS assessment is one in which UPDRS Part III has been completed in the ON state. The UPDRS assessment utilized as the baseline will be the later of the Screening or

Baseline visit assessment that is valid.

The selected assessment will be used to determine the Baseline UPDRS Parts I – IV subscores and the UPDRS I-IV total score. If a valid UPDRS is not available at Screening or Baseline visit, then the subject will be excluded from “change from baseline” UPDRS summary statistics.

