9.6.1. Exploratory Variables

The exploratory variables including the change from Baseline (where applicable) will be summarized using descriptive statistics by visit:

1. UPDRS Part II (ADL subscale) + Part III (motor subscale) total score
2. UPDRS Part II (ADL subscale) score
3. UPDRS Part III (motor subscale) score in the ON state
4. UPDRS Part I total score
5. UPDRS Part IV total score
6. Dyskinesia as measured by questions 32, 33 and 34 of UPDRS Part IV
7. Motor fluctuations as measured by question 39 of UPDRS Part IV
8. Clinical Global Impression of Improvement (CGI-I)
9. Patient's Global Impression of Improvement (PGI-I)
10. Parkinson's Disease Quality of Life Questionnaire (PDQ-39; total score and individual domain scores)
11. Non-motor Symptom Assessment Scale
12. Patient-completed diaries (Change from Baseline in the number of hours per day spent as follows: OFF, ON time without troublesome dyskinesia, total ON time, ON time with troublesome dyskinesia and asleep time)
13. Healthcare Resource Utilization
14. EuroQol 5D-5L Health Questionnaire (EQ-5D-5L)
15. Fall questionnaire

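### The SAP accepts only an ON-state UPDRS Part III exam as baseline, then lets OFF or fluctuating exams into later summaries still labelled ON state

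*SAP*

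**What the plan says.** - **Baseline (SAP 5.5).** "A valid UPDRS assessment is one in which UPDRS Part III has been completed in the ON state". The later valid assessment from Screening or Baseline supplies the Parts I-IV "subscores and the UPDRS I-IV total score". The section continues: "If a valid UPDRS is not available at Screening or Baseline visit, then the subject will be excluded" (from the UPDRS change-from-baseline summaries).
- **Inclusion in summaries (SAP 9).** For ESS and UPDRS III, the SAP recognises that sites may have collected data in OFF or fluctuating. It treats those data as compliant: "we will not check for the subject being in the “ON” state before including in summary statistics".
- **Change from baseline (SAP 5.8).** Post-baseline value minus baseline, with no condition on motor state.
- **Variable label (SAP 9.6.1).** "UPDRS Part III (motor subscale) score in the ON state", summarized by visit with change from baseline.
- **Conduct rule.** SAP Table 1, footnote i: "UPDRS to be measured in ON state". Protocol 7.2: "UPDRS Part III in OFF will not be evaluated".
- **Recorded state (Protocol Appendix 15.1).** After Part III the form asks for the patient's state during the exam. The options are On, "Fluctuated during the exam", and Off.

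**The concern.** The plan applies a strict state rule on one side of the subtraction and none on the other. Higher Part III scores mean worse motor function, and OFF is when medication has stopped helping. Letting OFF and fluctuating exams in after an ON-only baseline therefore pushes the mean change toward worsening. With one arm, no comparator carries the same contamination and cancels it.

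A reader of a table headed ON state would take it as ON-only. The SAP requires no footnote, no count of non-ON exams by visit, and no motor-state column in a listing, so the reader could not gauge the extent of the mix. The Part II + III total is affected through its Part III component.

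The ESS part of the same SAP 9 sentence is not at issue. That questionnaire asks about the patient's usual recent life, and its form has no state item.

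**Working it through.** **1. The rules side by side**

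| Step | Rule on motor state | Source |
|---|---|---|
| Baseline Part III | ON only; otherwise excluded from change summaries | SAP 5.5 |
| Post-baseline Part III | Any state in the database | SAP 9 |
| Change | Post-baseline minus baseline, no state condition | SAP 5.8 |
| Label | ON state | SAP 9.6.1 |

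The SAP 9 sentence is not expressly limited to post-baseline visits. If it also covered baseline, the validity test and exclusion in SAP 5.5 would have no effect. The reading that keeps both sections in force is that the specific rule (5.5) governs baseline and the general rule (9) governs later visits. The computed quantity is then any-state minus ON-only.

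**2. Is the state available?** The form in Appendix 15.1 records it, SAP 9 names the non-ON states, and SAP 5.5 as written needs it. The eCRF itself is not in the documents, so capture is very likely rather than proven.

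**3. Size.** The plan states no figure on this point. The only figure taken from it below is the enrolment of 450. Everything else is assumed:

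- p = share of non-ON exams at a visit, 2-10%, with 20% as an extreme
- d = mean excess of those exams over the same patients' ON score, 5-15 points, with 20 as an extreme
- w = how much worse those patients would score even in ON, 0-5 points
- ON SD = 8-12 points, taken as equal in both states

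Shift in the mean from admitting non-ON exams = p × d:

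| p | d | Shift (points) |
|---|---|---|
| 0.02 | 5 | 0.10 |
| 0.05 | 10 | 0.50 |
| 0.10 | 15 | 1.50 |
| 0.20 | 20 | 4.0 |

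**4. Bias from excluding them instead.** Let the ON patients have mean m. The target, the ON mean over all examined patients, is m + pw.

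- ON-only minus target = −pw; at most −0.10 × 5 = −0.50.
- All-data minus target = m + p(w + d) − (m + pw) = +pd.
- Gap between the two tables = p(w + d); for example 0.05 × (2.5 + 10) = 0.625.

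With d and w both at least 0, the two tables bracket the target.

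**5. Precision of the visit mean.** Before exclusion, SE = √(SD² + p(1 − p)d²)/√450. After exclusion, SE = SD/√(450(1 − p)). This ignores w.

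| SD | p | d | SE before | SE after | Ratio |
|---|---|---|---|---|---|
| 8 | 0.10 | 15 | 9.18/√450 = 0.433 | 8/√405 = 0.398 | 0.919 |
| 8 | 0.05 | 10 | 0.391 | 0.387 | 0.990 |
| 8 | 0.02 | 5 | 0.379 | 0.381 | 1.006 |
| 12 | 0.10 | 5 | 0.570 | 0.596 | 1.046 |

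Exams lost at a fully attended visit: 450 × 0.02 = 9 to 450 × 0.10 = 45. In the extreme case (20%, 20 points, SD 8) the loss is 90 and the ratio is 0.422/0.533 = 0.79.

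**The case against.** **The asymmetry is an inference.** Read literally, SAP 9 deems every exam in the database compliant, including Screening and Baseline, so the change would be any-state minus any-state. It is true that the SAP never says which section prevails. But this reading nullifies the ON condition in SAP 5.5 and still leaves the ON label false, so an edit is needed either way.

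**The waiver is open, prespecified and defensible.** Keeping all observed data avoids informative exclusion, and the SAP does not impute missing data. This has weight, and it is the reason to retain the all-data table. It does not justify the label.

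**Traceability exists elsewhere.** SAP 9.3.3 lists the last anti-PD dose with the date and time of Part III, and deviations are at least listed under SAP 9.2. Neither section names motor state as an item, so neither guarantees that a reader can identify the non-ON exams.

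**The magnitudes are assumed.** They are. Fluctuating exams probably carry a smaller excess than OFF exams. The protocol's timing of Part III after levodopa and the form's instruction to re-examine unstable patients should keep p low. The 4.0-point case is an outer bound, not an expectation.

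**A relabel plus a count would suffice.** That would make the table honest. It would not make the change score compare like with like while SAP 5.5 keeps an ON-only baseline.

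**Conclusion.** The inconsistency is real. As written, the plan produces an ON-labelled Part III table that may contain OFF and fluctuating exams. On the reading that gives both sections effect, it also produces a change from baseline that mixes states. That the label is false whenever a non-ON exam is included does not depend on any assumption. The asymmetry depends on SAP 5.5 governing baseline.

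The expected direction is apparent worsening. The plausible size is 0.10 to 1.50 points in the mean, under the assumed 2-10% of non-ON exams and 5-15 points of excess.

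The consequence is limited. These are exploratory summaries with no formal tests, and no primary safety conclusion, error rate or sample size changes. It should be corrected because the remedy is simple and the label is misleading, but it does not threaten the study's main purpose.

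**What to change.** In SAP 9, replace the waiver as it applies to UPDRS III:

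1. The ON-state Part III summary and the Part II + III summary use only exams recorded as ON on the UPDRS form, at every visit.
2. The number of non-ON exams is reported by visit, and the recorded state is a column in the UPDRS listing.
3. The all-data summary is kept as a supportive table, because exclusion may be informative and missing data are not imputed.
4. SAP 5.5 is stated to govern selection of the baseline assessment for Parts I-IV. After baseline, Parts I, II and IV, which rest on past-week recall, are summarized on their own whatever the state during the Part III exam.

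The ESS wording can stay.

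The cost is a few SAP sentences, one listing column, one count row per visit and one supportive table. No new data collection is needed if the form's state item is in the eCRF. Under the assumed 2-10%, the ON-only table loses 9 to 45 of 450 patients at a fully attended visit. The standard error changes by a factor of about 0.92 to 1.05, so precision may improve or worsen slightly.

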9.1. Subject Disposition

Subject disposition data will be summarized for all patients who entered into [TOZ-CL06](#). A table will include:

- Number of patients screened
- Number of patients enrolled
- Number (%) of patients who completed the study
- Number (%) of patients in the FAS

- Number (%) of patients in the SS
- Number (%) of patients in the mFAS
- Number (%) of patients in the xPK
- Number (%) of patients out of those who enrolled who early discontinued along with reasons for withdrawal
- Number (%) of patients out of those who enrolled who terminated early because of program termination

The percentages (%) will be calculated using ‘Number of patients enrolled’ in the denominator.

A listing of all patients who enrolled along with data on their disposition will be provided.

A table will be presented to summarize the number and percent of patients enrolled at each site by region, country and all patients.

A table will be presented to summarize the number and percent of patients who attended each study visit.

9.2. Protocol Deviations and Violations

Protocol deviations and violations (PDVs) will be identified and categorized as major or minor by the Sponsor prior to database lock.

If there is a significant number of major protocol deviations and violations, they will be summarized by deviation/violation category. Otherwise, all PDVs will be documented in a data listing only.

9.3. Treatments

9.3.1. Extent of Study Drug Exposure

The number of days of exposure to study drug and average daily dose (mg/day) will be summarized by study visit in the SS. Average daily dose will be calculated as (number of tablets dispensed minus the number of tablets returned minus the number of tablets lost) divided by number of days from visit i-1 to visit i and multiplied by the mg of the tablets. The proportion of subjects who took 60mg, 120mg will be summarized by study visit in the SS. Subjects who took only 60mg doses from visit i-1 to visit i will be included in the numerator for the 60mg category for visit i; subjects who took only 120mg doses from visit i-1 to visit i will be included in the numerator for the 120mg category for visit i. Descriptive statistics for the total number of tablets dispensed, number of tablets returned and number of tablets lost will be displayed by study visit and overall. Compliance with study drug will be calculated as (number of tablets dispensed minus the number of tablets returned minus the number of tablets lost) divided by the scheduled number of doses, expressed as a percentage. If this percentage is calculated greater than 100%, then compliance will be calculated 1 minus (the calculated percentage minus 1). Compliance will be summarized overall and by scheduled weeks for the safety analysis set.

Study drug dispense and accountability with the reason for not returning tablets is captured on the CRF and will be presented in the data listings.

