6.2.3.4 Assignment and Dispensing of Investigational Medicinal Product

Note: Sites participating in Expanded PK Sampling should refer to [Appendix 15.9.1](#) for Assignment and Dispensing of IMP instructions.

1. For patients meeting all entry criteria, complete the IMP assignment transaction using the IXRS by following the procedures provided.
 - a. Dispense the open-label IMP bottle(s) assigned by the IXRS to the patient for this study visit. Each bottle consists of either 50 tablets of 120 mg tozadenant or 100 tablets of 60 mg tozadenant.
 - b. Record the date IMP was dispensed in IMP dispensing records including patient number, assigned IMP bottle number(s), and date and time IMP was dispensed.
 - c. Review the dosing instructions for the IMP with the patient, answer any questions, and remind the patient to return the IMP (including all used, unused and partially used bottles) at the next visit.
 - d. Patients will be instructed to take either two (2) 60 mg tablets or one (1) 120 mg tablet of the dispensed IMP by mouth BID, in the morning and in the evening preferably at the same time each day, for a total of either two (2) 120 mg tablets or four (4) 60 mg tablets per day. The evening dose should be approximately 12 hours after the morning dose. Patients will be instructed to take their morning and evening doses 1 hour before or 2 hours after a meal and to refrain from eating for 1 hour after dosing. Patients should take the first dose of IMP at home after the Baseline Visit.
2. Instruct the patient to take the first dose of IMP at home on the evening of dispensation.
3. Ensure that the patient understood the dosing instructions and the use of the extra doses included in the bottle if visit delayed and/or use of visit window.
4. Schedule the Week 2 visit. If needed, use the visit window in relation to the date of the Baseline visit.

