 - CGI-I.
 - PGI-I.

- c. Have the patient complete the following self-assessment questionnaire:
 - ESS.
9. Administer the following assessments (may be done anytime during visit):
 - a. C-SSRS.
 - b. mMIDI. (Note: After Baseline, if patient has one or more positive modules on the mMIDI, their continued participation in the study should be discussed with the Medical Monitor.)
 - c. Assessment for episodes of sudden onset of sleep.
 - d. Healthcare Resource Utilization.
10. Collect the IMP (including all used, unused and partially used bottles) dispensed at the Baseline Visit.
 - a. Record the date and approximate time when the patient took the last dose of IMP.
 - b. Assess and document IMP accountability and compliance (document any missed dose(s), lost tablets and number of tablets taken).
 - c. Review and reconcile any discrepancies with the patient.
11. Dispense the open-label IMP bottle(s) assigned by the IXRS to the patient for this study visit. Each bottle consists of either 100 × 60 mg tablets or 50 × 120 mg tablets.
 - a. Record the date IMP was dispensed in IMP dispensing records.
12. Review the dosing instructions for the IMP with the patient, answer any questions, and remind the patient to return the IMP (including all used, unused and partially used bottles) at the next visit.
13. Ensure that the patient understood the dosing instructions and the use of extra doses included in the bottle if visit delayed and/or use of visit window.
14. Schedule the next study visit (Week 4). If needed, use the visit window in relation to the date of the Baseline visit.

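### The exposure and compliance formulas count a bottle entered as neither returned nor lost as fully taken, which can print about 429 mg/day at Week 2 against a permitted maximum of 240

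*SAP*

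**What the plan says.** SAP 9.3.1 (Extent of Study Drug Exposure) defines two quantities with the same numerator.

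- Average daily dose: "Average daily dose will be calculated as (number of tablets dispensed minus the number of tablets returned minus the number of tablets lost", then "divided by number of days from visit i-1 to visit i and multiplied by the mg of the tablets". It is summarized by study visit in the Safety Set.
- Compliance: "Compliance with study drug will be calculated as (number of tablets dispensed minus the number of tablets returned minus the number of tablets lost", then "divided by the scheduled number of doses, expressed as a percentage". It is summarized overall and by scheduled week. A fold-back applies above 100%: "If this percentage is calculated greater than 100%, then compliance will be calculated 1 minus (the calculated percentage minus 1".

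The SAP expects that some tablets will not come back, because "accountability with the reason for not returning tablets is captured on the CRF and will be presented in the data listings". That reason does not enter either formula.

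The protocol collects more than the formula uses. Section 5.8 requires all supplies back at each visit, with accountability done in the patient's presence. Section 6.2.4, item 10, has the site "document any missed dose(s), lost tablets and number of tablets taken" and reconcile discrepancies, and the later dispensing visits repeat this. Bottles hold spare tablets by design: section 6.2.3.4 refers to "the use of the extra doses included in the bottle if visit delayed and/or use of visit window". The same section has bottle numbers recorded at dispensing.

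**The concern.** A tablet can end an interval in one of four states: swallowed, returned, lost, or still at the patient's home. The numerator has terms for the second and third, and everything else is treated as swallowed. A bottle left at home therefore adds its unused tablets, including the spares packed for the visit window, to the dose taken. Lost does not clearly cover this case. Protocol 5.7 explains loss as breakage or wastage, and the SAP does not define it.

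This is a single-arm safety study, so the exposure table tells the reader what dose the adverse event, laboratory and ECG results belong to. An average dose above the highest permitted dose would look like overuse, and the summary table could not separate real overuse from a forgotten bottle.

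**Working it through.** **Inputs**

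- Bottle content: 50 tablets of 120 mg or 100 of 60 mg (protocol 6.2.3.4), which is 6000 mg either way.
- Starting regimen: two 120 mg or four 60 mg tablets per day (6.2.3.4), so 240 mg/day. Only 60 and 120 mg BID are permitted (3.1), so 240 is also the maximum.
- Baseline to Week 2: 14 days, window plus or minus 3 days (protocol Table 1), so 11 to 17 days.
- Assumptions: one bottle dispensed at Baseline (the protocol leaves the number open; 50 tablets at 2 per day last 25 days, which covers 17), and two 120 mg bottles at Week 2.
- The patient takes every dose: 28 tablets of 120 mg in 14 days, 22 left.

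**1. The formula works when the bottle comes back.** (50 - 22 - 0) / 14 x 120 = 240 mg/day. With 60 mg tablets: (100 - 44 - 0) / 14 x 60 = 240 mg/day. Both match the regimen.

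**2. Bottle not brought back, entered as 0 returned and 0 lost.**

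| Visit day | Average daily dose (mg/day) | Raw compliance (120 mg tablets) |
|---|---|---|
| 11 | 50 x 120 / 11 = 545 | 50 / 22 = 227% |
| 14 | 50 x 120 / 14 = 429 | 50 / 28 = 179% |
| 17 | 50 x 120 / 17 = 353 | 50 / 34 = 147% |

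On day 14 the excess is 429 / 240 = 1.79 times the maximum. The 60 mg bottle gives the same dose: 100 x 60 / 14 = 429.

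**3. The result depends on how the site enters the bottle.** The patient's behaviour is identical in each row.

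| Entry | Result (mg/day) |
|---|---|
| 0 returned, 0 lost | 429 |
| 0 returned, 22 lost | (50 - 22) / 14 x 120 = 240 |
| 0 returned, 50 lost | 0 |
| Returned count left blank | Missing, since SAP 9 does not impute missing data |

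**4. Bottle comes back at Week 6.** The SAP does not say which interval gets the credit. If it is the visit of return, Weeks 2 to 6 have 100 dispensed and 44 + 22 = 66 returned, so 34 tablets count as taken: 34 x 120 / 28 = 146 mg/day, and 34 / 56 = 61% compliance. The truth is 240 and 100%. Over both intervals the error cancels: 150 - 66 = 84 tablets against 84 scheduled doses in 42 days, so 100%.

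**5. Bottle never comes back.** The 22 spare tablets remain in the overall count. Over 52 weeks (364 days, 728 doses) that is 22 / 728 = 3% of overall compliance.

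**6. Effect on the Week 2 table.** The documents give no non-return rate, so the share f below is an assumption. All patients are fully adherent on day 14. Mean = 240 + 188.6f and SD = 188.6 x sqrt(f(1 - f)), where 188.6 = 428.6 - 240.

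| f | Mean (mg/day) | Spurious SD | Mean raw compliance, 100 + 78.6f |
|---|---|---|---|
| 2% | 244 | 26 | 102% |
| 5% | 249 | 41 | 104% |
| 10% | 259 | 57 | 108% |

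The median stays at 240. One such record with a 14-day interval puts the reported maximum at 429 or more.

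**The case against.** The strongest reply is that the effect is narrow and partly self-limiting, and much of that stands.

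- **It depends on data entry.** The 429 mg/day needs an entered zero. A reader might infer that every forgotten bottle produces it. The documents do not show how the CRF codes non-return, and a blank would leave the interval missing.
- **A second affected interval is not certain.** A reader might infer that one bottle always distorts two intervals. That holds only if a late return is credited when received, which the SAP does not state. Recorded bottle numbers would allow it to be matched to its own interval.
- **Non-return is discouraged.** Supplies are due back at every visit, and calls before Weeks 12, 24 and 52 remind patients to bring them (protocol 6.2.9, 6.2.13, 6.2.17). No such call is listed before Week 2.
- **No planned safety analysis uses these values.** No analysis set in SAP 3.1 depends on compliance, adverse events are counted by subject, and no tests are run. Days of exposure and the 60/120 mg categories do not use this numerator. Dispensed, returned and lost counts are tabulated and the reason for non-return is listed, so a forgotten bottle can be traced.
- **Part of any compliance distortion belongs to another rule.** The 179% would print as 2 - 1.786 = 21% because of the fold-back, and mean compliance would then fall below 100%. On the numerator alone it rises. The low figures should not be charged to this point.

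None of this supplies the missing rule. The SAP captures a reason for non-return and has no step that acts on it, and average daily dose has no cap or exclusion.

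**Conclusion.** The point holds in a limited form. As written, the SAP 9.3.1 numerator gives a wrong dose for a bottle entered as neither returned nor lost: about 429 mg/day at Week 2 for a patient taking 240 (353 to 545 over the window), with raw compliance of 179%. This rests on one bottle dispensed at Baseline, zeros in both the returned and lost fields, and full adherence. The Weeks 2 to 6 figures of 146 mg/day and 61% further assume two bottles at Week 2 and credit at the visit of return. In that case overall compliance corrects itself.

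The consequence is confined to the by-visit mean, SD and maximum of the exposure and compliance tables. At assumed rates of 2 to 10% the Week 2 mean moves by 4 to 19 mg/day and the median does not move. A reader might go further and conclude that the safety results themselves are compromised. The documents do not support that, because no safety summary is computed from these values. The change is still worth making: it is cheap, and it keeps doses that were never taken out of the exposure table.

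**What to change.** In SAP 9.3.1:

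1. Keep dispensed minus returned minus lost for any interval in which every bottle dispensed is accounted for.
2. When a bottle is unaccounted for, do not count its tablets as taken. Use the reconciled tablets-taken count if the eCRF holds it. Otherwise set that interval's average daily dose and compliance to missing, and report the number of such patients per visit.
3. Credit a late-returned bottle, matched by bottle number, to the interval in which it was dispensed.
4. State how an unreturned bottle is coded and that it is not entered as lost by default.

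Replacing the pill count with the tablets-taken count throughout is not needed. With all bottles back, the pill count is the more objective measure.

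The cost is SAP wording and one derivation change, with no new study procedure. The documents do not confirm that the tablets-taken count reaches the eCRF, so check this first. If it does not, the missing-interval rule works alone. The downside is that a few intervals become missing, possibly more often in poorer adherers, which could tilt compliance upward. Reporting the count per visit makes that visible. Any tablets-taken count used relies partly on patient report.
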